2.2 Efficacy evaluation

2.2.1 Definition of geographic region for efficacy analyses

Centers/countries with a small number of patients will be pooled to create geographic regions. Larger centers/countries will be considered as their own geographic region. There are six geographic regions planned: Europe, Latin America, South-East Asia, East Asia, Australia and Africa. The pooling of centers and/or countries to create geographic regions will be confirmed once all patients have been randomized. The allocation of countries to the specific geographic regions will be as follows.

Centers/Countries	Geographic region
AUT, BGR, CZE, DEU, ESP, EST, FIN, HUN, ISR, ITA, LTU, LVA, NOR, POL, ROU, RUS, SVK, TUR	Europe
ARG, BRA, COL, DOM, GTM, MEX, PAN, PER	Latin America
IND, MYS, PHL	South-East Asia
HKG, KOR, TWN	East Asia

AUS	Australia
ZAF	Africa

2.2.2 Primary efficacy variables

2.2.2.1 Variable definition

The primary efficacy variable is time to confirmed initial treatment failure. The confirmed initial treatment failure is defined as a patient with HbA1c measurements $\geq 7.0\%$ at two consecutive scheduled visits (after remapping in [section 1.3.3](#) has been applied), starting from Visit 4 (Week 13). The time to confirmed initial treatment failure is defined as the time from randomization until the time when the second of the two HbA1c measurement $\geq 7.0\%$ was determined after at least 13 weeks of treatment (Visit 4), i.e. the end of Period 1. The rationale of starting the treatment failures count from Visit 4 is that treatment guidelines consider as treatment failure patients who do not achieve HbA1c $< 7.0\%$ after 3 months of treatment ([ADA-EASD, 2009](#)).

The main study conclusion will be based on the analysis of the primary efficacy variable using the FAS. Analyses based on the PPS will also be performed to assess the robustness of the conclusion.

2.2.2.2 Handling of missing values/censoring/discontinuations

In the analysis for the primary efficacy variable of time to treatment failure, patients who discontinue the study for any reason during Period 1 (lack of efficacy, lost to follow-up, AE or abnormal laboratory values etc.) will be treated as censored values at the time of discontinuation. Patients who remain under the threshold (or whose measurement above the threshold is not confirmed at next scheduled visit) will be censored at the time of last study visit.

No imputation will be used for missing HbA1c measurements. As detailed in [section 1.3.3](#), re-defined scheduled visits will be created and so it should be the case that there is always a measurement for a scheduled visit, as an unscheduled visit should be carried out to ensure there was an HbA1c value available. However, if there is a case where the HbA1c value is missing then when looking for consecutive scheduled visits, only visits with non-missing HbA1c measurements will be considered (e.g. if Visit 4 HbA1c $\geq 7.0\%$, Visit 5 HbA1c is missing, and Visit 6 HbA1c $\geq 7.0\%$, then this will be considered treatment failure).

2.2.2.3 Statistical model, hypothesis, and method of analysis

Time to initial treatment failure

The primary statistical hypothesis of time to initial treatment failure will be assessed by a 1-sided test of superiority of the combination treatment with vildagliptin + metformin versus metformin monotherapy with α -level of 0.025 with a null hypothesis that the hazard-ratio between the combination treatment vildagliptin + metformin and metformin monotherapy is equal or greater than 1, versus the 1-sided alternative hypothesis that the hazard-ratio is less than 1:

$H_0: \lambda_{\text{vildagliptin+metformin}}/\lambda_{\text{metformin}} \geq 1$

versus

$H_a: \lambda_{\text{vildagliptin+metformin}}/\lambda_{\text{metformin}} < 1$

where $\lambda_{\text{vildagliptin+metformin}}$ and $\lambda_{\text{metformin}}$ are the hazard-rates of the initial treatment failure for vildagliptin 50mg bid + metformin up to 1000mg bid and metformin up to 1000mg bid monotherapy respectively.

The time to confirmed failure will be derived as the time from randomization to the second of two consecutive scheduled visits (after remapping in [section 1.3.3](#) has been applied), at which HbA1c $\geq 7.0\%$ is measured, starting from Visit 4 (13 weeks after randomization).

The primary efficacy analysis will use a Cox proportional hazard regression model to assess the probability of initial treatment failure, with treatment approach and geographic region as classification variables and baseline HbA1c as a covariate. The hazard-ratio and associated 95% confidence interval as well as the p-value estimated from the above model will be presented by treatment approach.

The initial treatment failure rate over time by treatment approach will be summarized using estimates and 95% confidence intervals from a Kaplan-Meier analysis. The Kaplan-Meier estimates will be plotted, with symbols to indicate censored values.

The primary analysis for this primary efficacy variable will be performed using the FAS. It will be performed in the PPS as supportive analysis as well.

The model assumptions will be checked by plotting the Schoenfeld residuals for the treatment effect obtained from the model against time. A random spread of residuals with no clear pattern will indicate that the proportional hazards assumption is valid. The results will be presented in CSR Section 16 table(s).

2.2.2.4 Supportive analyses

Time to first treatment failure

The time to first treatment failure will be derived as the time from randomization to the first of two consecutive scheduled visits (after remapping in [section 1.3.3](#) has been applied), at which HbA1c $\geq 7.0\%$ is measured, starting from Visit 4 (13 weeks after randomization).

Time to first treatment failure will be analyzed in the similar way as primary analysis.

Time to second treatment failure

The time to second treatment failure will be derived as the time from randomization to the second of the two consecutive scheduled visits (after remapping in [section 1.3.3](#) has been applied), at which HbA1c $\geq 7.0\%$ is measured in period 2.

Patients who discontinue the study for any reason during Period 1 or period 2 without the treatment failure are censored at the date of discontinuation. Patients that failed (2 consecutive scheduled visits with $\geq 7\%$) in period 1 and didn't failed in period 2 are at the end of period 2. Patients who didn't failed in period 1 passed to period 3 are censored to last study visit prior period 3.

Time to the second treatment failure will be analyzed in the similar way as primary analysis.

Descriptive analysis in HbA1c over time

Summaries of absolute values and change from baseline to end of Period 1 in HbA1c by treatment approach and visit will be presented in the FAS. Figures will be produced showing the mean HbA1c and standard error by visit during the study Period 1 for each treatment approach. The summary table and figure will be repeated for PPS.

In addition, the above descriptive analysis (including summary table and figure) will be performed for FAS on HbA1c data collected up to the end of Period 2, as well as data collected during the entire duration of the study.

Subgroup analysis

Summaries of absolute values and changes from baseline to end of Period 1 in HbA1c will be presented by treatment approach. The analysis will be performed on FAS. The list of subgroups of interest is listed below:

1. Baseline HbA1c category (<7%, ≥7%).
2. BMI (<30kg/m², ≥30kg/m² at Visit 1).
3. Age at Visit 1 by tertiles i.e. < 48 years, 48-< 62 years, ≥ 62 years.
4. Gender.
5. Race.
6. Smoking status
7. Geographical regions

In addition to above mentioned subgroups, following will be analyzed and reported for time to confirmed treatment failure endpoint in the same way as defined for the primary analysis.

- Age (three subgroups per tertiles of baseline age in all patients pooling the two treatment groups) (i.e., ≤ P33 years, >P33 - ≤ P66 years and > P66 years)
- Age (< 65 years, ≥ 65 years)
- Baseline GFR [mL/min/1.73m²] (<90, ≥90), baseline GFR (<60, ≥60), baseline GFR (<30, 30-<60, 60-<90).

Other baseline demographic subgroups may be added as appropriate.

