Time to insulin initiation	The time to insulin initiation is defined as the time from randomization (Visit 3) to the date of initiation of insulin therapy prescribed in Period 3 (i.e. for treatment intensification according to local guidelines) or to the date of discontinuation from the study in Period 2 due to not being able or unwillingness to initiate insulin therapy for treatment intensification in Period 3 (see Section 9.5.2.2).
Treatment-naïve patient	Patients not having ever received any anti-diabetic medication, or patients who, after the diagnosis of T2DM ≤ 24 months ago, have received anti-

	diabetic medication cumulatively for not more than 3 months, and have not received any anti-diabetic treatment within 3 months prior to Visit 1 (only metformin up to 2000mg daily is allowed within 1 month prior to Visit 1).
Variable	Information used in the data analysis; derived directly or indirectly from data collected using specified assessments at specified time points.

Amendment 4

Amendment rationale

The protocol is being amended based on a health authority request to incorporate the redefined order of analysis in the protocol to align with the final, published statistical analysis plan. The loss of glycaemic control was analysed as a secondary endpoint instead of a primary endpoint, and an additional detail was provided for the confirmatory visit for the primary analysis of time to initial treatment failure. Following this, only one primary endpoint approach was included in the statistical analysis plan analysis and the multiple testing method was removed.

Changes to the protocol

The second primary endpoint was removed from [Section 2.1](#) and moved to [Section 2.2](#) as a secondary endpoint. References to appropriate sections in the statements were updated.

In [Section 6.4](#), the second primary endpoint was removed and entered as a secondary endpoint.

In [Section 9.4.1](#) and [Section 9.4.2](#) only the remaining primary endpoint was described, and reference to the (previously existing) second primary endpoint was removed. The text was further adjusted to clarify the initial treatment failure (confirmed by the second of the two HbA1c measurements $\geq 7.0\%$). Text referring to the (previously existing) second primary endpoint was removed from [Section 9.4.3](#). In [Section 9.4.4](#) the time to first treatment failure was clarified, as well as the descriptive subgroup analysis.

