3.1.3 Period 2: vildagliptin/metformin combination versus vildagliptin add-on to metformin

In the case of two consecutive HbA1c measurements $\geq 7.0\%$ from two consecutive study visits during Period 1, scheduled according to [Table 6-1](#) & [Table 6-2](#), patients in both arms will receive new vildagliptin study medication packs. The investigator will contact the IRT system within 2 weeks after the receipt of the second of the two elevated HbA1c measurements. The IRT system will assign the new vildagliptin study medication packs. Patients who were randomised to the placebo arm in Period 1 will now receive vildagliptin 50mg bid. Patients who were randomised to the active vildagliptin 50mg bid arm in Period 1 will continue to receive vildagliptin 50mg bid. All patients will continue to take their metformin dose unchanged. Period 2 will remain masked to the patient and both patients and investigators will remain masked to the treatment allocation in Period 1.

Any anti-diabetic medication other than the study regimen is not allowed during Period 2, except if the patient had temporarily reduced/interrupted the treatment regimen due to AEs or untoward events that require temporary dose adjustment/interruption (see [Section 5.5.5](#)).

If, during Period 2, therapy intensification is required in accordance with the local guidelines, the patient will enter Period 3.

The duration of Period 2 may differ between patients. End of Period 2 is considered when insulin treatment is initiated, or alternatively when the patient is discontinued because insulin treatment is not initiated in Period 3 (see [Section 3.1.4](#)).

[figure not shown]

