1.2 Last On-Treatment Observation (Endpoint Observation)

For specified efficacy variables, clinical laboratory variables, vital signs and ECG findings, the measurement obtained at the last post-baseline study visit will be considered the last on-treatment (endpoint) observation, regardless of whether it is obtained at a scheduled or unscheduled visit, up to the last scheduled visit.

For specified efficacy variables, clinical laboratory variables and ECG findings, end of Period 1 and end of Period 2 endpoints will also be of interest. The end of Period 1 endpoint is defined as the final available post-randomization assessment obtained at any visit (scheduled or unscheduled), prior to or at initial treatment failure, up to the last scheduled study visit. The end of Period 2 endpoint is defined as the final available post-randomization assessment

obtained at any visit (scheduled or unscheduled), prior to or at the initiation of insulin therapy, up to the last scheduled study visit.

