2.1.6 Study medication

The study consists of three treatment periods.

In Period 1 patients will be randomized to metformin + vildagliptin 50mg bid, or metformin + placebo. If initial treatment fails to maintain HbA1c < 7.0%, confirmed at two consecutive scheduled study visits (after remapping in [section 1.3.3](#) has been applied), starting from Visit 4 (Week 13), then vildagliptin will be added to metformin in the metformin-only arm in Period 2. The Period 1 end date is defined as the date of the second of the two consecutive scheduled study visits, i.e. the initial treatment failure date. The Period 2 start date is defined as the next day.

In Period 3, insulin is considered based on local guidelines. Both patients and investigators will remain masked to the treatment allocation in Period 1, and the study will compare the two different treatment approaches. The Period 3 start date is defined as the date of insulin initiation. The Period 2 end date is defined as the previous day.

Treatments are referred to as ‘Treatment approach’ throughout this analysis plan to acknowledge that patients are not on the same treatment for the duration of the study. When summaries are detailed for the ‘Treatment Period’, they will include data from Periods 1, 2 and 3, unless specified otherwise.

The duration of exposure to study medication (in months) during the treatment period will be computed for all patients using the algorithm outlined in [Section 1.4](#) and summarized by treatment approach for the RAN both descriptively (i.e., mean, standard deviation, median, minimum and maximum) and by 3 - monthly intervals (0 - < 3 months, 3 - < 6 months, ..., ≥ 60 months).

The study Period 1 duration (in months) will be also similarly summarized for the RAN. The study Period 1 duration is defined as (initial treatment failure date – treatment start date + 1)/30.4375 for patients who entered study Period 2. The study Period 1 duration is the same as overall study duration for patients who did not enter into Period 2.

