This analysis is performed in the FAS only. Data collected up to the end of Period 1, or the end of Period 2, or to the end of the study will be used in the analysis for assessing the rate of change from Visit 4 to end of Period 1, or from Visit 4 to end of Period 2, or from Visit 4 to the end of the study respectively.

A general downward trend from Visit 4 to the end of study can be assumed for these parameters.

[figure not shown]
Variables related to the rate of loss in glyceic control over time

The rate of loss in glyceic control in HbA1c or FPG from 26 weeks after the start of Period 2 to the end of Period 2 will be assessed for patients who start insulin therapy in Period 3 (i.e. for treatment intensification) or discontinue the study during Period 2 due to not being able or unwilling to initiate insulin therapy in Period 3. The random coefficient linear mixed effect model used in the primary efficacy endpoint 'rate of loss in glyceic control in HbA1c from Visit 5 (Week 26) to the end of Period 1' will be used in this secondary variable. Only data collected between initiation of Period 2 to insulin initiation on patients who take insulin therapy in Period 3 (i.e. for treatment intensification) or who discontinued the study in Period 2 due to not being able or unwilling to initiate insulin therapy in Period 3 will be included in this model. Patients who complete the study in Period 1 or Period 2 will not be included in the analysis. The analysis will be performed in the FAS only. Note that it is not known how many patients will proceed into Period 3, so may need to later review whether the planned analysis for the subgroup of patients entering Period 3 (or being unable/unwilling to) is sensible.

The rate of loss in glyceic control in FPG from 26 weeks to the end of Period 1 will be assessed using the same random coefficient linear mixed effect model used in the primary efficacy endpoint 'rate of loss in glyceic control in HbA1c from Visit 5 (Week 26) to the end of Period 1'. This analysis is performed in the FAS only.

[figure not shown]
Variables related to change from baseline to endpoint

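### The post-hoc time-to-second-failure analysis censors as non-failing those Period 2 patients who start insulin, or leave because needed insulin was not started, before a second high HbA1c is recorded

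*SAP*

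**What the plan says.** **Event.** In SAP Addendum 1, Section 2.2.2.4, time runs from randomization to the second of two consecutive scheduled visits with HbA1c of at least 7.0%, where the result "is measured in period 2". I read this as requiring both values in Period 2.

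**Censoring.** The same section has three rules:
- Patients who discontinue in Period 1 or 2 "without the treatment failure are censored at the date of discontinuation", whatever the reason.
- Patients who failed in Period 1 and not "failed in period 2 are at the end of period 2".
- Patients who reach Period 3 without a Period 1 failure are censored at the last visit before Period 3.

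The analysis otherwise follows the primary one (Cox and Kaplan-Meier). SAP Section 2.8 calls it post-hoc and says it goes into the clinical study report.

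**End of Period 2.** Protocol 3.1.3 states: "End of Period 2 is considered when insulin treatment is initiated, or alternatively when the patient is discontinued because insulin treatment is not initiated". The trigger for moving on is local guidelines, not the two-visit 7.0% rule. SAP 2.1.6 starts Period 3 on the day of insulin initiation and adds: "The Period 2 end date is defined as the previous day". SAP 1.2 takes the end-of-Period-2 assessment as the last one "prior to or at the initiation of insulin therapy, up to the last scheduled study visit".

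**Time to insulin initiation.** The protocol glossary runs this endpoint to the start of Period 3 insulin "or to the date of discontinuation from the study in Period 2 due to not being able or unwillingness to initiate insulin therapy". SAP Addendum 1, Section 2.2.3.2 lists it as a variable.

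**The concern.** Cox and Kaplan-Meier estimates assume that a censored patient has the same outlook as those who stay under observation. A patient whose treatment had to be intensified, or who left because it had to be and was not, has a worse outlook. If this happens before the confirming HbA1c, the analysis records a patient without second failure and removes that patient from the risk set at the point of deterioration.

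The arms may also differ in how often it happens. On entering Period 2 the metformin arm gains vildagliptin, while the combination arm continues the regimen on which it failed (Protocol 3.1.3 and 5.2). A difference in early intensification is therefore plausible, though the documents do not show one. A failure curve and hazard ratio will be reported, and no composite, competing-event or sensitivity analysis is specified for this endpoint.

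**Working it through.** The plan gives no event count, rate or power for this endpoint, so there is no figure to reproduce.

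**Step 1: who can be lost.** Visits are 13 weeks apart (Protocol 3.2), and Period 2 starts the day after a scheduled visit (SAP 2.1.6). Two scheduled Period 2 values therefore take about 2 × 13 = 26 weeks. A patient who starts insulin sooner will normally be censored and cannot become an event. Later in Period 2, a patient who starts insulin between a first high value and its confirmation is lost in the same way. A patient with two high values before insulin is an event.

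One edge case: if the confirming sample is drawn on the day insulin starts, it falls outside Period 2 under SAP 2.1.6, while the SAP 1.2 wording would include it.

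**Step 2: approximate effect.** Let q be the share of second failures that end in insulin start, or in leaving because needed insulin was not started, before confirmation. The recorded hazard in an arm is then about (1 − q) times the full one, so

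observed HR ≈ HR × (1 − q_combination)/(1 − q_metformin).

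**Step 3: illustrative simulation**, 200,000 patients per arm, treatment-only Cox model, 5 years.
- From SAP 2.7: 10% initial failure at 13 weeks; 7.1% annual failure on metformin (hazard −ln(1 − 0.071) = 0.0736 per year); Period 1 hazard ratio 0.75; 4% yearly dropout (Version 3.0).
- Assumed: a Period 2 deterioration hazard h2 of 0.2 or 0.5 per year, equal in both arms; q from 0 to 40%; confirmation 0.25 year after the first high value; pre-empting insulin at 0.125 year.

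The composite counts insulin start, or leaving because needed insulin was not started, as an event.

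Equal q in both arms:

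| h2 | q | Metformin 5-year rate, SAP rule | Composite | HR, SAP rule | HR, composite |
|---|---|---|---|---|---|
| 0.2 | 10% | 12.7% | 14.1% | 0.855 | 0.853 |
| 0.2 | 40% | 8.7% | 14.2% | 0.866 | 0.858 |
| 0.5 | 10% | 21.4% | 23.6% | 0.844 | 0.843 |
| 0.5 | 40% | 14.7% | 23.6% | 0.861 | 0.851 |

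The rate falls short by about q (for example 14.7/23.6 = 0.62 at q = 40%). The hazard ratio moves by 0.01 or less.

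Unequal q (hazard ratios for h2 = 0.2 and 0.5):

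| q metformin / combination | Formula factor | HR, SAP rule | HR, composite |
|---|---|---|---|
| 10% / 20% | 0.80/0.90 = 0.89 | 0.77, 0.75 | 0.87, 0.85 |
| 20% / 10% | 0.90/0.80 = 1.13 | 0.96, 0.96 | 0.85, 0.85 |
| 20% / 40% | 0.60/0.80 = 0.75 | 0.66, 0.64 | 0.87, 0.85 |
| 40% / 20% | 0.80/0.60 = 1.33 | 1.14, 1.11 | 0.85, 0.83 |

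The simulated ratios agree with the formula, for example 0.959/0.852 = 1.13.

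**Step 4: who is censored harmlessly.** In the simulation 29% (h2 = 0.5) to 53% (h2 = 0.2) of patients entering Period 2 were still in it without an event at week 260. Their censoring is administrative.

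**The case against.** The strongest reply is that second failure is a laboratory endpoint with an objective threshold, and time to insulin initiation is a separate listed variable that already captures insulin start and leaving because insulin was not started. Merging the two mixes a central-laboratory criterion with local decisions. The censoring also follows the primary endpoint's convention, which censors all Period 1 discontinuations, including those for lack of efficacy (SAP 2.2.2.2). This stands as an argument for keeping the HbA1c-only version. It does not make the censoring uninformative.

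The protocol's definition could lead a reader to infer that every end of Period 2 is a treatment failure. The SAP does not support that. Its Period 2 slope analysis says "Patients who complete the study in Period 1 or Period 2 will not be included in the analysis", so patients can finish the study in Period 2. Others leave for adverse events, withdrawn consent or other reasons in Protocol 5.5.9.

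A reader might also infer that the clearest second failures are removed. They are not: two high values before insulin still count. Some patients who leave without starting insulin may also be counted, because the withdrawal visit includes HbA1c (Protocol Section 6) and is assigned to the closest unallocated visit (SAP 1.3.2).

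Nor do the documents say that insulin may follow a single high value; they refer only to local guidelines, which they do not reproduce.

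**Conclusion.** The point holds in a limited form. Among patients with a Period 1 failure, those moved to insulin for intensification, or leaving because needed insulin was not started, before two Period 2 values of at least 7.0% are treated as non-failing. That censoring follows glycaemic worsening. The Kaplan-Meier rate is then too low, whether the target is failure had insulin not intervened or failure including the need for insulin. The first case assumes that these patients were likelier than others to have had a confirming value.

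The shortfall is roughly q, and the documents do not allow q to be derived. A reader might infer a hazard-ratio bias in a known direction. The documents do not support this: with equal q the ratio barely moves, and with unequal q it can move either way. All q and h2 values above are assumptions. The different handling in the time-to-insulin endpoint shows that an alternative is available; it is not a contradiction, because the endpoints differ. The analysis is post-hoc and supportive, so the primary conclusion is untouched.

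**What to change.** In SAP 2.2.2.4:

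1. Keep the HbA1c-only analysis and restore the missing word *censored*.
2. State that patients who complete the study in Period 2 without failure are censored at their last study visit. SAP 2.8 already uses this rule for time to insulin initiation.
3. Add an analysis with the same Cox and Kaplan-Meier methods. Among patients with a confirmed Period 1 failure, it counts insulin initiation for treatment intensification, or Period 2 discontinuation because needed insulin was not started, as a second-failure event on that date.
4. Keep the existing rule for patients who reach Period 3 without a Period 1 failure, so that nobody has a second failure without a first.
5. Report both versions side by side, with the number per arm censored in the HbA1c-only version for each of the two reasons.

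The cost is SAP wording, one extra event flag and a small set of outputs. Insulin dates and discontinuation reasons are already collected. The added composite partly overlaps with time to insulin initiation and, like the endpoint itself, would be labelled post-hoc.

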9.6 Sample size calculation

A total sample size of 1000 randomised patients per treatment arm (in 1:1 allocation ratio to vildagliptin + metformin and metformin monotherapy) is planned.

Power calculation for the time-to-treatment failure variable

The sample size calculation assumes that all randomised patients are to be followed up for 5 years unless patients dropped out from the study for various reasons (lack of efficacy, AEs,

abnormal labs, lost to follow-up etc.), and that the yearly dropout rate is 11% (estimate based on ADOPT data (Kahn S et al, 2006)).

The existing vildagliptin study data suggest that approximately 10% of vildagliptin patients will have an HbA1c >7.0% after the first 3 months of the study (initial response phase), since those patients who are randomised with an HbA1c measurement above the failure threshold (7.0%) may never have an HbA1c measurement below the required threshold during the study and will therefore be counted as failures during the first 13 weeks. A similar proportion is assumed for the comparator arm. Hence it is expected that the difference in failure rate is likely to be small early in the study, but will diverge as the study progresses. The power calculations have been adjusted to take this assumption into account using statistical simulations.

The simulations showed that assuming an annual initial treatment failure rate of 7.1% in the metformin monotherapy arm (estimated based on ADOPT data), incorporating a 10% initial failure rate after 13 weeks in each treatment arm (due to some patients with BL HbA1c $\geq 7.0\%$), 1000 patients per treatment arm would be sufficient to detect a hazard-ratio of 0.75 between vildagliptin + metformin and metformin alone (corresponding to a risk reduction rate of 25% in vildagliptin + metformin group *versus* metformin alone) with approximate 66% power and a 1-sided significance level of 0.025 (corresponding to a 2-sided test at 0.05).

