2.7 Determination of sample size

A total sample size of 1000 randomized patients per treatment arm (in 1:1 allocation ratio to vildagliptin + metformin and metformin monotherapy) is planned.

The sample size calculation assumed that all randomized patients are to be followed up for 5 years unless patients dropped out from the study for various reasons (lack of efficacy, AEs, abnormal labs, lost to follow-up etc.). Including the updated information of the yearly dropout rate being approximately 4% (based on observed discontinuation rate for this study at the time of completion of the trial).

The existing vildagliptin study data suggest that approximately 10% of vildagliptin patients will have an HbA1c >7.0% after the first 3 months of the study (initial response phase), since those patients who are randomized with an HbA1c measurement above the failure threshold (7.0%) may never have an HbA1c measurement below the required threshold during the study and will therefore be counted as failures during the first 13 weeks. A similar proportion is assumed for the comparator arm. Hence it is expected that the difference in failure rate is likely to be small early in the study, but will diverge as the study progresses. The power calculations have been adjusted to take this assumption into account using statistical simulations.

The simulations showed that assuming an annual initial treatment failure rate of 7.1% in the metformin monotherapy arm (estimated based on ADOPT data), incorporating a 10% initial failure rate after 13 weeks in each treatment arm (due to some patients with baseline HbA1c $\geq 7.0\%$), 1000 patients per treatment arm would be sufficient to detect a hazard-ratio of 0.75 between vildagliptin + metformin and metformin alone (corresponding to a risk reduction rate of 25% in vildagliptin + metformin group versus metformin alone) with approximate 75% power and a 1-sided significance level of 0.025 (corresponding to a 2-sided test at 0.05).

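### SAP Addendum 1 carries the primary Cox analysis into age and GFR subgroups without a treatment-by-subgroup interaction, so the level p-values cannot show whether the effect differs

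*SAP*

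**What the plan says.** The protocol (9.4.4) and SAP V3.0 (2.2.2.4) call the subgroup analysis descriptive and limit it to summaries of HbA1c values and changes. SAP Addendum 1 (2.2.2.4) drops that label and adds the primary endpoint: "following will be analyzed and reported for time to confirmed treatment failure endpoint in the same way as defined for the primary analysis".

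The groups it lists are:
- age in three groups, given as "Age (three subgroups per tertiles of baseline age in all patients pooling the two treatment groups", cut at P33 and P66;
- age below 65 or 65 and over;
- baseline GFR below 90 or 90 and over;
- baseline GFR below 60 or 60 and over;
- baseline GFR below 30, 30 to below 60, and 60 to below 90.

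The list is left open: "Other baseline demographic subgroups may be added as appropriate".

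The primary analysis (Addendum 1, 2.2.2.3) is a Cox model with treatment approach, region and baseline HbA1c. It tests superiority at one-sided 0.025 and reports a hazard ratio, 95% confidence interval and p-value. The only interaction named in either document is treatment by time, in the HbA1c slope model. The Addendum's document history and section 2.8 label the subgroup analysis of the primary endpoint post hoc, for inclusion in the study report.

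**The concern.** A p-value within a level asks whether the effect is distinguishable from none in that level. It does not ask whether the effect differs between levels, and it depends heavily on how many events the level contains. If one age group is significant and its neighbour is not, the result invites a claim that age or renal function modifies the effect, although that pattern is expected by chance under a single hazard ratio. The protocol (1.2) says the results may support guideline groups, so a misreading of this kind could travel. The plan gives the reader no direct test of difference and no statement of how consistency will be judged.

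**Working it through.** **Inputs from the documents.** Protocol 9.6: 1000 patients per arm "would be sufficient to detect a hazard-ratio of 0.75", "with approximate 66% power and a 1-sided significance level of 0.025 (corresponding to a 2-sided test at 0.05". It assumes 7.1% annual failure on metformin, 10% early failure per arm at 13 weeks, 11% yearly dropout and 5 years of follow-up. SAP V3.0 (2.7) keeps these but uses about 4% dropout and arrives at a design "with approximate 75% power". Addendum 1 (2.7) also gives 75% but with 11% dropout. Both powers are carried through below.

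**Reproducing the stated power.** Log-rank simulation, 5000 runs per case, early failures with no treatment effect, exponential hazards −ln(1−0.071) for failure and −ln(1−dropout) for dropout, follow-up to 5.25 years:
- 11% dropout: 64.2% and 65.9% under two ways of coding the early failures (stated 66%), about 570–590 events.
- 4% dropout: 75.8% and 76.1% (stated 75%), about 645–667 events.

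Stricter readings of the follow-up gave 58–60% and 68–70%.

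**Power within a level.** With overall power P, the mean of the overall test statistic is 1.96 + z(P). For a level holding a share s of the information, the mean is that value times √s, and power p = Φ(mean − 1.96).

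- P = 0.75: 1.96 + 0.674 = 2.634. Tertile: 2.634/√3 = 1.521, p = Φ(−0.439) = 0.330. Half: 2.634/√2 = 1.863, p = Φ(−0.097) = 0.461.
- P = 0.66: 1.96 + 0.412 = 2.372. Tertile: 2.372/√3 = 1.370, p = Φ(−0.590) = 0.278. Half: 2.372/√2 = 1.677, p = Φ(−0.283) = 0.389.

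**Chance of mixed p-values under one hazard ratio.** For k equal, independent levels this is 1 − p^k − (1−p)^k.

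| Overall power | Tertiles: power per level | Tertiles: mixed | Halves: power per level | Halves: mixed |
|---|---|---|---|---|
| 66% | 28% | 60% | 39% | 48% |
| 75% | 33% | 66% | 46% | 50% |

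At 75%, for tertiles: 1 − 0.330³ − 0.670³ = 0.66. All three tertiles are significant in only 0.330³ = 4% of trials (2% at 66% power). Direct simulation of random tertiles gave 59–60% mixed at 11% dropout and 67–68% at 4%. More power does not cure this within a realistic range: at 90% overall, p = 0.465 and the tertiles are mixed in 75% of trials.

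**What an interaction test would do.** In the same simulations a heterogeneity test across tertiles at 0.05 flagged the constant effect in 4.7–5.6% of trials. Its power is modest. For a 50:50 split the standard error of the log ratio of hazard ratios is √(16/events), so with 570–646 events the power is 40–45% for a ratio of 0.75 and 86–90% for 0.60. Over three factors, the chance of at least one false flag is 1 − 0.95³ = 14% if they were independent.

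**Counting the levels.** The list gives 3 + 2 + 2 + 2 + 3 = 12. Protocol 4.2 (criterion 4b) excludes a calculated clearance below 60 at Visit 1. Baseline GFR is re-derived from Day 1 values (SAP 1.10), so a few patients may fall below 60, but the levels below 60, below 30 and 30 to below 60 should be nearly empty. Then 60 and over is nearly the whole FAS, and 60 to below 90 nearly repeats below 90. About 3 + 2 + 2 = 7 informative levels remain. The three-level GFR grouping has no level for 90 and over, so it does not cover the FAS.

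**The case against.** The analysis is supportive and openly post hoc, and the main conclusion rests on the primary FAS analysis. The text does not literally prescribe one model per level, and it sets no subgroup hypothesis, alpha or decision rule. Hazard ratios and intervals would be reported too, and a careful reader judges consistency from those. The suggested test is weak and brings its own multiplicity, and a non-significant interaction may be over-read as proof of consistency.

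Most of this stands as a limit on consequence. It does not supply the missing comparison: p-values come with the output, no other method is given, and nothing says they are not to be compared.

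Three stronger readings are tempting and should not be drawn:
- **That the two age groupings contradict each other.** The same section labels fixed cuts "Age at Visit 1 by tertiles i.e" below 48, 48 to below 62, and 62 and over, and then lists P33/P66 groups. With age in whole years, P33 = 47 and P66 = 61 would make the two sets identical. The age distribution is not in the documents, so they do not show that either set is not tertiles.
- **That there are 12 separate informative tests.** The overlap and the GFR exclusion rule this out.
- **That a constant effect will usually look inconsistent on any factor.** This is so for tertile p-values. For one evenly split factor it is about an even chance.

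**Conclusion.** The point holds as a gap in method. The level p-values cannot show whether the effect varies by age or GFR, and under one common hazard ratio they would be mixed in about 60–66% of trials for age tertiles and about half for a 50:50 factor. These figures assume equal, independent levels, overall power as stated (66–75%), and significance judged at one-sided 0.025. Actual level sizes are not in the documents, and unequal splits change the figures: at 75% power a 20:80 split has exactly one level significant in 59% of trials. The primary conclusion is untouched. This is a cheap improvement to a post-hoc analysis, worth making because the results go into the study report.

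**What to change.** For each factor whose levels cover the FAS and have enough events (age tertiles, age 65, GFR below 90 or 90 and over), fit one Cox model in the FAS with treatment, factor, treatment-by-factor, region and baseline HbA1c. Show the hazard ratio and 95% confidence interval per level in a forest plot, with one interaction p-value per factor labelled nominal, post hoc, low-powered and unadjusted for multiplicity. State that within-level p-values are not used to judge consistency, and that a non-significant interaction does not establish it.

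For GFR below 60 or 60 and over, and for the three-level grouping, add the missing level of 90 and over or merge sparse levels, and give estimates only where events allow.

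The cost is SAP wording and one model per factor in place of one per level. No new data are needed.
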